8.3. Clinical Laboratory Tests

8.3.1. Laboratory Value Definitions

Laboratory values and change from baseline values will be summarized descriptively by visit. The baseline value will be determined using the last nonmissing value collected before the first dose using the priority defined in [Table 7](#). The last record before administration in the highest

priority will be considered the baseline record. For baseline laboratory candidates with the same date and time in the same priority category, the in-window value will be used as the baseline.

Table 7: Baseline Laboratory Identification

Priority	Laboratory Visit	Proximity to Visit Window	Tiebreaker
1	Scheduled	In-window	Use smallest laboratory sequence number
2	Unscheduled	In-window	
3	Scheduled	Out-of-window	

Laboratory test values outside the normal range will be assessed for severity based on CTCAE grade or similar criteria where clinical intervention is required for CTCAE grading. The incidence of abnormal laboratory values and shift tables relative to baseline will be tabulated.

8.3.2. Laboratory Value Summaries

Local laboratories will be used for this study. Any laboratory test results and associated normal ranges from local laboratories will be converted to SI units. If a tie still exists, the laboratory value with the smallest laboratory sequence number will be used in by-visit summaries. [Table 8](#) will be used to determine the record used for by-visit tabulations and summaries.

Table 8: Identification of Records for Postbaseline By-Visit Summaries

Priority	Laboratory Visit	Proximity to Visit Window	Tiebreaker
1	Scheduled	In-window	Use smallest laboratory sequence number
2	Unscheduled	In-window	
3	Scheduled	Out-of-window	

Numeric laboratory values will be summarized descriptively in SI units; non-numeric test values will be tabulated when necessary. In addition, line graphs may be provided for alanine aminotransferase, alkaline phosphatase, total bilirubin, alkaline phosphatase, amylase, lipase, creatinine, blood urea nitrogen, hematocrit, hemoglobin, absolute neutrophil count, platelets, T3, Free T3, thyroxine, thyroid stimulating hormone, absolute lymphocyte count, white blood cell counts (leukocytes), troponin I, and troponin T.

Severity grades will be assigned to laboratory test values based on the numerical component of CTCAE v5.0. Shift tables will be presented showing change in CTCAE grade from baseline to worst grade postbaseline. Separate summaries for abnormally high and abnormally low laboratory values will be provided when the laboratory parameter has both high and low grading criteria. The denominator for the percentage calculation will be the number of participants in the baseline category. The number of participants who experienced worsening of laboratory abnormalities will be summarized by maximum severity.

8.3.3. Potential Hy's Law Events

Participants with elevated alanine aminotransferase or aspartate aminotransferase (ie, $\geq 3 \times$ ULN range and alkaline phosphatase $< 2 \times$ ULN range), accompanied by total bilirubin $\geq 2 \times$ ULN range at the same visit, will be listed by treatment group.

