Brain MRI or CT	X*						X†	X†	X†		*Screening brain imaging should be performed on all participants who have previous history of CNS metastasis or as clinically indicated (eg, based on clinical symptoms). On-study brain imaging will be performed only if the screening brain imaging was positive or as clinically indicated. †If indicated, brain imaging should occur at same time as disease assessment scans. Whenever feasible, contrast-enhanced brain MRI is preferred to CT. See Section 8.2 for details.

Table 4: Schedule of Laboratory Assessments

Procedure	Screening	Treatment				EOT	Safety Follow-Up	Notes
	Days -28 to -1	Cycle 1		Cycle 2+			EOT + 30 and 90 days (± 7 d)	
		Day 1	Day 15 (± 3 d)	Day 1 (± 3 d)	Day 15 (± 3 d)			
Local laboratory assessments								
Blood chemistries	X	X*	X	X		X	X†	*Only required at Cycle 1 Day 1 if screening assessment was not performed within 7 days. † 30-day visit only.
Hematology with differential	X	X*	X	X		X	X†	
Fasting lipid panel	X			X		X		Performed at screening, Cycle 2 Day 1, Day 1 of every third cycle thereafter (ie, Cycles 5, 8, etc), and EOT.
Coagulation panel	X			X		X		
Urinalysis	X			X		X		
Thyroid function panel	X			X		X		Performed at screening, Day 1 of every even cycle (ie, Cycles 2, 4, etc), and EOT. Note: Participants may be administered study treatment in subsequent cycles after Cycle 1 Day 1 while thyroid test results are pending.
Hepatitis screening	X							Results obtained within the last 3 months before Cycle 1 Day 1 are acceptable.
TnI or TnT monitoring	X	X*	X	X†	X‡	X		*Only required at Cycle 1 Day 1 if screening assessment was not performed within 3 days. †Cycles 2, 3, and 4 only. ‡Cycles 2 and 3 only. Note: To be performed within 3 calendar days prior to dose administration and all labs should be checked prior to dose administration. Note: Day 15 labs should be checked as soon as possible. In case of high troponin, perform cardiac imaging via echocardiography with/without cardiac MRI.

Table 4: Schedule of Laboratory Assessments (Continued)

Procedure	Screening	Treatment				EOT	Safety Follow-Up	Notes
	Days –28 to -1	Cycle 1		Cycle 2+			EOT + 30 and 90 days (± 7 d)	
		Day 1	Day 15 (± 3 d)	Day 1 (± 3 d)	Day 15 (± 3 d)			
Local laboratory assessments (continued)								

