	Grades 2 or 3	Withhold until \leq Grade 1.	
 Consider prompt initiation of standard antidiarrheal agents and other necessary supportive care as needed (eg, oral and/or IV fluids). Administer systemic corticosteroids per local practice followed by taper. Consider prophylactic antibiotics per local practice. Consider gastrointestinal consultation and performing endoscopy to rule out colitis.
	Grade 4 or recurrent Grade 3	Permanently discontinue.	
AST/ALT elevation and/or increased total bilirubin/hepatitis	Grade 1	No action.	
 Administer systemic corticosteroids per local practice followed by taper. Consider monitoring liver enzymes weekly (or more frequently) until liver enzyme value returns to baseline or is stable. Consider monitoring total bilirubin, direct bilirubin, and alkaline phosphatase weekly (or more frequently) if needed.
	Grade 2 ALT or AST increase or Total bilirubin increases to $> 1.5 \times$ and up to $3 \times$ ULN	Withhold.	
	Grades 3 or 4 ALT or AST increase or In participants with liver metastases with baseline Grade 2 elevation of AST or ALT, hepatitis with AST or ALT increases $\geq 50\%$ and lasts ≥ 1 week or Total bilirubin increases to $> 3 \times$ ULN	Permanently discontinue.	

Table 11: Guidelines for Management of Immune-Related Adverse Events (Continued)

irAE	Toxicity Grade or Conditions (CTCAE v5.0)	Action Taken With Study Treatment	Adverse Event Management With Corticosteroid and/or Other Supportive Care Therapies
Endocrinopathies 
 Type 1 diabetes mellitus Hyperglycemia Hyperthyroidism Hypothyroidism Adrenal insufficiency 	Grades 1 and 2	No action if clinically appropriate.	None.
	Grade 2 adrenal insufficiency	Withhold until \leq Grade 1 or otherwise clinically stable	Initiate treatment with HRT as clinically indicated.
	Grades 3 and 4 adrenal insufficiency	Withhold until \leq Grade 1 after corticosteroid taper to \leq 10 mg/day prednisone or equivalent or is otherwise clinically stable.	Initial dose of 1 to 2 mg/kg/day prednisone or equivalent followed by a taper and HRT as clinically indicated.
	Grades 3 and 4 hypothyroidism	Withhold until \leq Grade 2 or is otherwise clinically stable.	Initiate thyroid replacement hormones (eg, levothyroxine or liothyronine) per SoC.
	Grades 3 and 4 hyperthyroidism	Withhold until \leq Grade 2 or is otherwise clinically stable.	Initiate symptomatic management.

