4.1.5. Cycle Length and Duration

Cycle 1 Day 1 is the day that the first dose of INCAGN02385, INCAGN02390, or retifanlimab is administered. The scheduled cycle length is 4 weeks. The actual Day 1 of subsequent cycles will correspond with the first day of administration of retifanlimab in that cycle.

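### The Hy's law listing needs every liver criterion at one visit, so a participant whose criteria never coincide at any single visit is not flagged

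*SAP*

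**What the plan says.** SAP 8.3.3 defines the listing in one sentence with three parts.

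- Transaminases: "Participants with elevated alanine aminotransferase or aspartate aminotransferase" of at least 3 x ULN. A parenthesis joins this threshold to an ALP below 2 x ULN ("ULN range and alkaline phosphatase").
- Bilirubin: the elevation must be "accompanied by total bilirubin" of at least 2 x ULN.
- Timing: "ULN range at the same visit, will be listed by treatment group".

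Neither document gives another Hy's law definition, a time window, or a rule for bilirubin that rises after the transaminases. Appendix A of the SAP has Listing 2.8.13 on potential drug-induced liver injury. It has no criteria of its own, so 8.3.3 presumably supplies them, but the SAP does not say so.

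Sampling is set by Protocol Table 4. The row "Blood chemistries" is marked at screening, Cycle 1 Day 1 (if screening chemistry is more than 7 days old), Cycle 1 Day 15, Day 1 of each later cycle, EOT and the 30-day follow-up. The Day 15 column is blank from Cycle 2. SAP 4.1.5 adds: "The scheduled cycle length is 4 weeks".

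For hepatic immune-related events, Protocol Table 11 (Section 6.5.3) advises: "Consider monitoring liver enzymes weekly (or more frequently) until liver enzyme value returns to baseline or is stable". A separate line reads: "Consider monitoring total bilirubin, direct bilirubin, and alkaline phosphatase weekly (or more frequently) if needed".

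**The concern.** A Hy's law listing is a screen, and its value lies in sensitivity. Transaminases and bilirubin need not peak together, and a rule that looks at one visit at a time sees only cases where the abnormal periods overlap at a draw. From Cycle 2 the scheduled draws are 4 weeks apart. Between them treatment may be withheld or stopped and corticosteroids given under Table 11, so transaminases can fall before bilirubin is next measured.

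What is at stake is how a negative result reads. An empty listing in one arm would naturally be taken to mean that no potential Hy's law case occurred, when it shows only that no participant met all criteria simultaneously. In a trial that adds one or two investigational checkpoint antibodies to a third, that distinction should be clear.

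**Working it through.** The plan states no figure to reproduce, and no power, alpha or event count is involved. The check is one of logic, followed by one piece of arithmetic on visit spacing.

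**Step 1. The two rules.**

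- Same-visit rule (SAP 8.3.3): list if, at some visit, max(ALT, AST) ≥ 3 and ALP < 2 and bilirubin ≥ 2, all in multiples of ULN.
- On-or-after rule (for comparison): list if, at some visit, max(ALT, AST) ≥ 3 and ALP < 2, and bilirubin ≥ 2 at that visit or a later one.

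**Step 2. Apply both to two-visit patterns.** The laboratory values are assumed and serve only to test the logic. Each cell gives ALT / AST / ALP / bilirubin in multiples of ULN.

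| Pattern | Visit 1 | Visit 2 | Same-visit | On-or-after |
|---|---|---|---|---|
| A. All criteria at one visit | 1 / 1 / 1 / 0.8 | 6 / 5 / 1.1 / 2.5 | listed | listed |
| B. Bilirubin later, ALT/AST still ≥ 3, ALP < 2 | 6 / 5 / 1.1 / 1.2 | 4 / 3.5 / 1.2 / 2.5 | listed | listed |
| C. Bilirubin later, ALT/AST now < 3 | 6 / 5 / 1.1 / 1.2 | 2.4 / 2.0 / 1.2 / 2.5 | **not listed** | listed |
| D. Bilirubin later, ALT/AST ≥ 3, ALP now ≥ 2 | 6 / 5 / 1.1 / 1.2 | 4 / 3.5 / 2.3 / 2.5 | **not listed** | listed |
| E. Transaminase rise only | 6 / 5 / 1.1 / 1.2 | 2 / 2 / 1.1 / 1.0 | not listed | not listed |

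The rules differ only in C and D. Pattern B matters as much: a later bilirubin rise does not by itself remove a participant from the listing.

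**Step 3. Missing analytes.** A draw without bilirubin or without ALP cannot satisfy the same-visit rule, whatever the enzymes show. Table 11 makes this possible by putting enzymes on one line and bilirubin with ALP on another, qualified by need. At scheduled visits it should not arise, because ALT, AST, ALP and total bilirubin all belong to the required chemistry panel in Protocol Table 14.

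**Step 4. Spacing of scheduled draws.** The cycle length is 28 days and Table 4 allows ±3 days around Day 1. The longest gap between consecutive Day 1 draws without a treatment delay is 28 + 3 + 3 = 34 days. A pairing window shorter than this would miss some pairs from adjacent cycles. Delays can lengthen the gap; Protocol 6.5.1 permits interruptions of up to 28 days, or longer with sponsor approval.

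**Step 5. Other displays.** Chemistry shift Table 3.3.2.2 and worsening Table 3.3.3.2 take one analyte at a time. Listings 2.8.2 and 2.8.8 hold all and abnormal chemistry values but do not pair transaminases with bilirubin. No Hy's law count table by arm is planned.

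**The case against.** The rule is explicit, internally consistent and contradicted by nothing else in the plan. It governs a descriptive listing and affects no endpoint, test or summary rate. The underlying data are well covered: Listings 2.8.2 and 2.8.8 are both marked for the DSMB package, whereas Listing 2.8.13 is not, so DSMB review does not depend on the same-visit condition. Liver events that stop treatment also appear in Table 3.2.16 and Listing 2.7.7.1. All of this stands. Affected cases are unpaired, not unreported.

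A reader might infer that anyone who reaches the thresholds at different visits is left out. The documents do not support that: pattern B is listed, because all criteria are met at the later visit.

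A reader might also try to put a percentage on the loss by assuming how long each abnormality lasts and how far bilirubin lags. The documents give no durations, lags or event rates. Any such figure would reflect its assumptions, above all whether follow-up draws are 4-weekly or weekly with a full panel. Table 11 does not mandate weekly checks, but it does invite them, and its second line covers bilirubin and ALP. Sampling on different days is possible; the documents do not show that it is common.

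Nor does SAP 8.3.3 exclude unscheduled samples. It does not define a visit, and Protocol 8.6 has unscheduled assessments recorded in the eCRF. The weakness there is silence, not exclusion.

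**Conclusion.** The point holds in limited form. Under SAP 8.3.3 a participant whose transaminase, ALP and bilirubin criteria never coincide at one visit is not flagged in the only planned display that pairs them. This follows from the wording of the rule and needs no assumption about rates. That it could happen in this trial rests on the 4-week spacing of scheduled chemistry from Cycle 2 and on the optional, separately worded follow-up monitoring.

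The size is small and cannot be quantified from the documents. The raw values stay available, and no efficacy or summary safety result changes. The practical risk is a negative liver-safety statement that claims more than the listing can show. It is worth correcting because the correction is cheap.

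**What to change.** In SAP 8.3.3:

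- List any participant with ALT or AST ≥ 3 x ULN and ALP < 2 x ULN who has total bilirubin ≥ 2 x ULN on the same date or within a prespecified window after that transaminase elevation.
- Have the sponsor set and justify the window. It should span two consecutive scheduled Day 1 draws, so at least 34 days; the documents do not fix a value beyond that, and delayed cycles deserve consideration.
- State that scheduled and unscheduled samples both count.
- Flag which rows are simultaneous, so the present definition can still be read off the listing.
- State that Listing 2.8.13 is this listing.

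The cost is a sentence or two in the SAP and a small program change, with no new data collection. The downside is a few extra rows for medical review, some of which will have other causes.

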8.4. Vital Signs

Values at each scheduled timepoint, change, and percentage change from baseline for vital signs, including systolic blood pressure, diastolic blood pressure, pulse, respiratory rate, body temperature, and body weight will be summarized descriptively.

Normal ranges for vital sign values are defined in [Table 9](#). For participants exhibiting vital sign abnormalities, the abnormal values will be listed along with their assigned treatment group. Alert vital signs are defined as an absolute value outside the defined normal range and percentage change greater than 25%. Note that the definition of alert vital signs does not apply for body temperature and weight. The abnormal values for participants exhibiting alert vital sign abnormalities will be listed.

Table 9: Normal Ranges for Vital Sign Values

Parameter	High Threshold	Low Threshold
Systolic blood pressure	≤ 155 mmHg	≥ 85 mmHg
Diastolic blood pressure	≤ 100 mmHg	≥ 40 mmHg
Pulse	≤ 100 bpm	≥ 45 bpm
Temperature	$\leq 38^{\circ}\text{C}$	$\geq 35.5^{\circ}\text{C}$
Respiratory rate	≤ 24 breaths/min	≥ 8 breaths/min

8.5. Electrocardiograms

Twelve-lead ECGs including heart rate, PR, QRS, QT, QTcF, and QTcB intervals will be obtained for each participant during the study. Values at each scheduled timepoint, change, and percentage change from baseline will be summarized for each ECG parameter. Baseline will be determined as the average of all nonmissing values before the first administration of study drug.

Normal ranges for ECG values are defined in [Table 10](#). Electrocardiogram values will also be considered abnormal if the absolute percentage change from baseline is more than 25% (30% for QRS interval). Participants exhibiting ECG abnormalities will be listed with study visit and assigned treatment group. Abnormal values for participants with alert ECG values, defined as both the absolute value and the percentage change from baseline being outside normal ranges, will be identified and listed. Outliers of QT, QTcB, and QTcF values, defined as absolute values > 500 milliseconds, > 460 milliseconds, or change from baseline > 30 milliseconds, will be summarized.

Table 10: Normal Ranges for Electrocardiogram Intervals

Parameter	High Threshold	Low Threshold
PR	≤ 220 ms	≥ 75 ms
QRS	≤ 120 ms	≥ 50 ms
QT	≤ 500 ms	≥ 300 ms
QTcF, QTcB	≤ 460 ms	≥ 295 ms
Heart rate	> 100 bpm	< 50 bpm

QTcB = Bazett's correction; QTcF = Fridericia's correction.

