 18. History of organ transplant, including allogeneic stem cell transplantation.
 19. Receiving probiotics as of the first dose of study treatment.
 20. History or presence of an abnormal ECG that, in the investigator's opinion, is clinically meaningful. Screening QTc interval > 460 milliseconds is excluded (corrected by Fridericia or Bazett formula). In the event that a single QTc is > 460 milliseconds, the participant may enroll if the average QTc for the 3 ECGs is ≤ 460 milliseconds.
 21. Has had a significant cardiac event within 6 months before the first dose of study treatment, including New York Heart Association Class III/IV, acute myocardial infarction (including severe/unstable angina), cardiomyopathy, coronary/peripheral artery bypass graft, symptomatic congestive heart failure, critical conduction delay, cerebrovascular accident or transient ischemic attack, or pulmonary embolism.

Note: Medically-controlled arrhythmia is permitted.

Note: Recovery from uncontrolled or Grade ≥ 3 hypertension to ≤ Grade 1 is required.

22. Has received a live vaccine within 30 days of planned start of study treatment.

Note: Examples of live vaccines include but are not limited to the following: measles, mumps, rubella, chicken pox/zoster, yellow fever, rabies, Bacillus Calmette–Guérin, and typhoid vaccine. Seasonal influenza vaccines for injection are generally killed virus

vaccines and are allowed; however, intranasal influenza vaccines are live-attenuated vaccines and are not allowed.

23. Known hypersensitivity to another monoclonal antibody that cannot be controlled with standard measures (eg, antihistamines and corticosteroids).
24. Known allergy or hypersensitivity to any component of either retifanlimab, INCAGN02385, or INCAGN02390 study drug formulation (including excipients and additives).
25. Women who are pregnant or breastfeeding.
26. Any condition that would, in the investigator's judgment, interfere with full participation in the study, including administration of study treatment and attending required study visits; pose a significant risk to the participant; or interfere with interpretation of study data.
27. The following participants are excluded in France: vulnerable populations according to article L.1121-6 of the French Public Health Code and adults under legal protection, or who are unable to express their consent per article L.1121-8 of the French Public Health Code.

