8.3.4. Electrocardiograms

Triplicate 12-lead ECGs will be obtained as outlined in [Table 3](#) at screening, Day 1 of Cycles 1 through 5, on Day 1 of every fourth cycle beginning at Cycle 9, at EOT, and as clinically indicated. All 12-lead ECGs will be performed with the participant in a recumbent or semirecumbent position after 5 minutes of rest.

All 12-lead ECGs will be performed using an ECG machine that automatically calculates the heart rate and measures PR, QRS, QT, and QTc intervals. Triplicate ECGs require 3 individual ECG tracings obtained as closely as possible in succession and up to approximately 2 minutes apart. The 12-lead ECGs will be interpreted by the investigator at the site to be used for immediate participant management. Additional 12-lead ECGs may be performed as clinically indicated to manage participant safety. The decision to include or exclude a participant or discontinue a participant from the study treatment based on an ECG flagged as "Abnormal, Clinically Significant" is the responsibility of the investigator, in consultation with the medical monitor, as appropriate. Clinically notable abnormalities that are considered clinically significant in the judgment of the investigator are to be reported as AEs. In the event that a single QTc is > 460 milliseconds at screening, the participant may enroll if the average QTc for the 3 ECGs is ≤ 460 milliseconds or with approval from the medical monitor. For participants with an intraventricular conduction delay (QRS interval > 120 milliseconds) at screening, the JTc interval may be used in place of the QTc with medical monitor approval. In addition, the JTc interval should be used for all subsequent assessments.

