2.8.5	Clinical Laboratory Values – Endocrine	X
2.8.6	Clinical Laboratory Values - Troponin	X
2.8.7	Abnormal Clinical Laboratory Values - Hematology	X
2.8.8	Abnormal Clinical Laboratory Values - Chemistry	X
2.8.9	Abnormal Clinical Laboratory Values - Coagulation	
2.8.10	Abnormal Clinical Laboratory Values - Urinalysis	
2.8.11	Abnormal Clinical Laboratory Values - Endocrine	X
2.8.12	Abnormal Clinical Laboratory Values - Troponin	X
2.8.13	Potential Drug-Induced Liver Injuries	
2.9.1	Vital Signs	
2.9.2	Abnormal Vital Sign Values	
2.9.3	Alert Vital Sign Values	
2.10.1	12-Lead ECG Values	
2.10.2	Abnormal 12-Lead ECG Values	
2.10.3	Alert 12-Lead ECG Values	
2.11.1	Body Weight

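### The SAP's two-part ECG alert rule omits some QTc values above 500 ms when baseline QTc exceeds 400 ms, and the heart-rate row of Table 10 is printed on the abnormal side

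*SAP*

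**What the plan says.** SAP 8.5 sets up three ways of flagging an ECG value.

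- **Abnormal.** A value is abnormal if it lies outside Table 10, where the upper limit for QTcF and QTcB is 460 ms. A change criterion is added: "Electrocardiogram values will also be considered abnormal if the absolute percentage change from baseline is more than 25% (30% for QRS interval"). The reporting is that "Participants exhibiting ECG abnormalities will be listed with study visit and assigned treatment group"; the planned output is Listing 2.10.2.
- **Alert.** A narrower class, "defined as both the absolute value and the percentage change from baseline being outside normal ranges". It has its own output, Listing 2.10.3, titled "Alert 12-Lead ECG Values".
- **QT/QTc outlier.** Values "defined as absolute values > 500 milliseconds, > 460 milliseconds, or change from baseline > 30 milliseconds, will be summarized". This is Table 3.5.8 and carries no percentage condition.

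On baseline, SAP 8.5 says "Baseline will be determined as the average of all nonmissing values before the first administration of study drug". Eligibility bounds it from above: Protocol 5.2 states "Screening QTc interval > 460 milliseconds is excluded", and Protocol 8.3.4 lets a participant with a single reading above the limit enroll if the triplicate average is "≤ 460 milliseconds or with approval from the medical monitor".

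Table 10 gives PR, QRS, QT and QTc as ≤ the high threshold and ≥ the low threshold. The heart-rate row alone reads > 100 bpm and < 50 bpm.

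**The concern.** A fixed 25% change is a demanding condition for QTc, because 25% of a baseline between 400 and 460 ms is 100 to 115 ms. A participant can exceed every outlier limit in the section and still not be an alert. The class whose name suggests the greatest concern then omits values that the outlier table in the same section singles out. Someone who reads only Listing 2.10.3 could find no QTc entry although QTc had exceeded 500 ms.

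The heart-rate row could err in the other direction. If programmed as the other rows are, it would put ordinary heart rates in the alert listing whenever they moved by more than 25%.

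**Working it through.** The documents state no figure for this point, so there is nothing to reproduce. The check is direct arithmetic.

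**Inputs.** From SAP 8.5: QTc upper limit 460 ms (Table 10), percentage limit 25%, both conditions required for an alert, and outlier limits of > 500 ms, > 460 ms or change > 30 ms. From Protocol 5.2: an entry ceiling of 460 ms.

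**Formula.** A high-side alert requires QTc > 460 and (QTc − baseline) / baseline > 0.25. Together these give QTc > max(460, 1.25 × baseline).

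| Baseline (ms) | 25% of baseline (ms) | Alert needs QTc above (ms) | Rise needed, more than (ms) | Values over 500 ms that are not alerts |
|---|---|---|---|---|
| 360 | 90 | 460 | 100 | none |
| 368 | 92 | 460 | 92 | none |
| 380 | 95 | 475 | 95 | none |
| 400 | 100 | 500 | 100 | none |
| 410 | 102.5 | 512.5 | 102.5 | over 500, up to 512.5 |
| 420 | 105 | 525 | 105 | over 500, up to 525 |
| 430 | 107.5 | 537.5 | 107.5 | over 500, up to 537.5 |
| 440 | 110 | 550 | 110 | over 500, up to 550 |
| 460 | 115 | 575 | 115 | over 500, up to 575 |

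**Smallest rise that can be an alert.** The two conditions meet where 1.25 × baseline = 460, that is at baseline 460 / 1.25 = 368 ms, where the rise must exceed 460 − 368 = 92 ms. Below 368 ms the 460 ms limit governs, and above it the 25% condition governs. Both require a larger rise, so 92 ms is the minimum, about three times the 30 ms outlier limit (92 / 30 = 3.1).

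**Where the omission begins.** 1.25 × baseline exceeds 500 only when baseline exceeds 500 / 1.25 = 400 ms. At or below 400 ms every QTc above 500 ms is an alert (501 from 400 is +25.2%).

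**Examples.**
- 430 to 520 ms: +90 ms, 90 / 430 = 20.9%. It meets all three outlier limits and is not an alert.
- 440 to 545 ms: +105 ms, 105 / 440 = 23.9%. It is not an alert.

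**How many participants could be affected.** The documents give no baseline QTc distribution. Assuming a normal distribution with SD 18 ms, the share with baseline above 400 ms is about 50%, 71%, 87% and 95% for means of 400, 410, 420 and 430 ms. This is the share for whom the gap exists. It is not the share of ECGs omitted, which also depends on on-treatment values.

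**Heart rate.** Read like the other rows, a normal value would have to be both > 100 and < 50 bpm, which is impossible. Every heart rate is then outside the range, the first alert condition is always met, and any change above 25% is an alert: 60 to 76 bpm is 16 / 60 = +26.7%. Table 9 in SAP 8.4 prints pulse the normal way round (≤ 100, ≥ 45 bpm).

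**The case against.** The strongest reply is that nothing goes unreported. Any QTc above 460 ms is in Listing 2.10.2 with visit and treatment group, values above 500 ms are counted in Table 3.5.8, and all readings are in Listing 2.10.1. Protocol 8.3.4 has the investigator interpret ECGs on site and report clinically significant abnormalities as AEs. The alert listing is not marked for the DSMB package, and no dosing, stopping or endpoint rule refers to it. SAP 8.4 uses the same two-part construction for vital signs, so it looks like a house convention. All of this stands, and it keeps the point small. It does not explain why a value can exceed all of the section's outlier limits without being an alert.

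On heart rate, one can say that > 100 and < 50 bpm under columns headed as thresholds plainly mark the abnormal side, so a programmer would probably not be misled. That is fair. The row still contradicts the table's title and its other rows.

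A reader might infer more than the documents support:

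- *That QTc values over 500 ms are generally left off the alert listing.* The gap needs a baseline above 400 ms and ends at 1.25 times baseline.
- *That marked prolongation would be hidden from the study report.* The other two outputs show it.
- *That the rule bears on a known QTc signal.* Amendment 1 says the extra ECGs were prompted by data from other LAG-3 agents and gives the same reason for troponin monitoring. It does not mention QTc. The cardiac events and guidance in the protocol concern pericardial effusion, myocarditis and troponin.

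**Conclusion.** The point holds in limited form. With baseline QTc above 400 ms, values from just over 500 ms up to 1.25 times baseline fall outside the alert class although they are abnormal and outliers under the same section. The gap is 25 ms wide at a baseline of 420, 50 ms at 440 and 75 ms at 460. It would be wider for anyone admitted above 460 ms under the Protocol 8.3.4 exception. The result is an inconsistent alert listing, with no loss of data and no effect on any efficacy conclusion. The heart-rate row is a separate printing error. Severity is minor.

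The QTc result rests on one inference: Table 10 has no normal range for percentage change, so the 25% in the preceding sentence is taken as that limit. The parallel rule for vital signs in SAP 8.4, which names 25%, supports this reading. The size in participants depends on a baseline distribution that the documents do not give.

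**What to change.** In SAP 8.5, count any QTcF or QTcB above 500 ms as an alert regardless of percentage change, and keep the existing two-part rule otherwise. The 500 ms limit is already in the section as an outlier limit, so no new threshold is introduced. A combined rule such as > 460 ms together with a rise > 30 ms would go further than the SAP, which joins those limits with or. In Table 10, print the heart-rate row as ≤ 100 bpm / ≥ 50 bpm.

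The cost is one sentence, one table row and one programming condition, with a slightly longer Listing 2.10.3. Some values between 460 and 500 ms will still be outliers without being alerts. That is the existing two-tier design, and Table 3.5.8 continues to cover them.
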